### **8.2.3 Subjects experiencing a flare in Part B**

All summaries will be based on observed case data and will use the FS, ie only subjects experiencing a flare based on the IXRS data will be included in these summaries. If deemed needed, further sensitivity analyses may be conducted excluding subjects incorrectly 'flared'.

#### **8.2.3.1 Continuous secondary efficacy variables**

For the continuous variables (ASDAS, BASDAI, BASFI, BASMI, SIJ SPARCC score and spine ASpiMRI-a in the Berlin modification score), descriptive statistics by randomized treatment group will be displayed. Summary tables will include the actual results at Week 96 (or later), as well as change from Part B Baseline.

These summary statistics will be repeated for Flare Baseline.

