### **2.2.1.2.3 Secondary efficacy variables for subjects who experience a flare in Part B**

These variables will be evaluated at Escape Week 12.

- ASDAS disease activity (ASDAS-ID, ASDAS-LD, ASDAS-HD, and ASDAS-vHD) and clinical improvement (ASDAS-CII, ASDAS-MI)
- ASAS20, ASAS40, ASAS5/6, and ASAS PR response
- Change from Part B Baseline in ASDAS, BASDAI, BASFI and BASMI
- Change from Part B Baseline in SIJ SPARCC and spine ASspiMRI-a in Berlin modification scores

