#### **2.3.3 Escape treatment**

Subjects experiencing a flare in Part B will be invited for an on-site visit to receive the next planned dose of investigational product (escape treatment). This visit will take place 2 weeks after the last assessment that resulted in meeting the flare criteria; or, at the discretion of the Investigator, at an earlier time point. As the start of escape treatment may vary from subject to subject, it will be referred to as “Escape Week 0”. Subjects will remain on the escape treatment for at least 12 weeks or until Week 96 of the regular visit schedule as described in Table 5.1 in the protocol, whichever is longer.

The assessment-schedule for subjects experiencing a flare in Part B will start 2 weeks after the flare condition is fulfilled; or, at the discretion of the Investigator, at an earlier time point and will end 2 weeks before Week 96 after Baseline of the regular assessment schedule. If the flare occurs late in Part B (at or after Week 82), the subject must receive the escape treatment for 12 weeks (eg, starting at Week 84 until Week 96). The final assessments at study end (as laid down for Week 96) must be performed 2 weeks after the last study dose administration accordingly.

Subjects receiving PBO or half-dose CZP (200mg Q4W) who experience a flare during the Double-Blind Period will escape to full-dose treatment (CZP 200mg Q2W) until the end of that period or for at least 12 weeks, whichever is longer. The escapers need to come back to the site at the time point of the escape (Week 0), 2 and 4 weeks after escape (Weeks 2 and 4), and every 12 weeks thereafter until the originally scheduled Week 96.

Subjects escaping from PBO to full-dose CZP (200mg Q2W) will receive a loading dose of CZP (400mg Q2W) at the 3 consecutive visits after the flare. Subjects escaping from half-dose CZP to full-dose CZP will receive CZP 200mg Q2W at the 3 consecutive visits after the flare. In order to maintain the blind, subjects escaping from half-dose CZP to full-dose CZP will receive a PBO-administration and a CZP 200mg administration at these 3 visits.

Subjects randomized to the CZP full-dose (200mg Q2W) treatment during the Double-Blind Period who qualify for escape will remain on their current treatment allocation. As with subjects escaping from half-dose CZP to full-dose CZP, these subjects will receive a PBO and CZP 200mg injection at the 3 visits after the flare in order to maintain the blind to the randomized treatment.

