The analysis time point of interest for subjects experiencing a flare in Part B is Escape Week 12. Additional time points of interest for this set of subjects are Escape Week 0, Escape Week 2, Escape Week 4, Escape Week 6, Escape Week 8, Escape Week 10, Escape Week 24, Escape Week 36 and the final assessment visit as laid down for Week 96. For subjects who complete the final assessment visit as laid down for Week 96, safety and efficacy data recorded at this visit will be included in summaries of the “Last Visit (Week 96 Termination)” visit and the “Last/Withdrawal Escape” visit if applicable. For subjects who withdraw prematurely from the Escape Part, data recorded at the Withdrawal Visit will be assigned to what would have been the next scheduled visit for the particular assessment that is being summarized, unless otherwise specified. These data will be included in the summaries of the assigned visit and the “Last/Withdrawal Escape” visit if applicable. If a subject withdraws early during the Escape Part but does not have a Withdrawal Visit, then safety and efficacy data recorded at either the date of the last scheduled or unscheduled visit during the Escape Part, whichever is later, will be included in summaries “Last/Withdrawal Escape” visit. Only post Flare baseline assessments will be included in the “Last/Withdrawal Escape” visit.

All visit measurements, even violating the visit window, will be utilized for the respective visit as long as they are in the proper sequence. In case of repeated assessments at a particular visit, the last assessment will be used for visit presentation in by-visit summaries (except unscheduled repeats of Week 96).

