#### **8.2.3.2 Binary secondary efficacy variables**

The number and percentage of subjects in the ASDAS disease activity levels (ASDAS-ID, ASDAS-LD, ASDAS-HD, ASDAS-vHD) as well as the number and percentage of subjects achieving ASDAS clinical improvement (ASDAS-CII, ASDAS-MI), and ASAS response (ASAS20, ASAS40, ASAS5/6, and ASAS PR) will be summarized at the Week 96 (or later) visit by randomized treatment group.

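### The secondary re-treatment variables are defined at Escape Week 12 but analysed at Week 96 or later, where time on escape treatment ranges from 12 to about 44–46 weeks

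*SAP*

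**What the plan says.** SAP section 2.2.1.2.3 introduces the secondary variables for subjects who flare in Part B (ASDAS activity states and improvement, ASAS responses, and changes in ASDAS, BASDAI, BASFI, BASMI and the two MRI scores) with "These variables will be evaluated at Escape Week 12". Section 3.3 agrees: "The analysis time point of interest for subjects experiencing a flare in Part B is Escape Week 12".

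The analysis sections for the same variables name another visit. Section 8.2.3.1, for the continuous variables: "Summary tables will include the actual results at Week 96 (or later), as well as change from Part B Baseline". Section 8.2.3.2, for the binary variables: they "will be summarized at the Week 96 (or later) visit by randomized treatment group". Neither mentions Escape Week 12.

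On how long escape lasts, section 2.3.3 says: "Subjects will remain on the escape treatment for at least 12 weeks or until Week 96 of the regular visit schedule", and it takes the longer of the two. On when it starts: "This visit will take place 2 weeks after the last assessment that resulted in meeting the flare criteria", or earlier if the investigator so decides.

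Section 3.10 lists the departures from the protocol-defined analyses, including a redefinition of Flare Baseline, but no change of time point for these variables. Section 8.3.3 summarises the same variables by visit after Escape Week 0, as other efficacy variables.

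**The concern.** One of the secondary objectives in section 2.1.2 is the efficacy of re-initiating full-dose treatment after a flare. A response at Escape Week 12 answers that at a fixed time since re-treatment began. A response at calendar Week 96 does not: it pools subjects who flared just after randomisation, and have had most of a year on escape, with subjects who flared near the end and have had only the minimum. A rate or mean change from that pool belongs to no particular duration of re-treatment.

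The SAP also leaves open which figure is the secondary result. A programmer working from section 2.2.1.2.3 and one working from section 8.2.3 would produce different tables under the same label. Unless the text is settled first, the choice could be made after the data are seen.

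**Working it through.** **The plan's own figure.** The only duration the SAP gives is the 12-week minimum, with an example in section 2.3.3 of escape from Week 84 to Week 96: 96 − 84 = 12 weeks. That reproduces.

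**Inputs.**
- Escape Week 0 = flare visit + lag, with a lag of 2 weeks, or less at the investigator's discretion (section 2.3.3). I take 0 to 2 weeks.
- Escape lasts to Week 96, and never less than 12 weeks (section 2.3.3).
- A single ASDAS above 3.5 at any Part B visit is a flare (section 3.2.22).
- Scheduled ASDAS visits are Weeks 50, 52, 56 and then every 4 weeks. This is read from the flare-date rules in section 3.2.23 (next visit 2 weeks after Weeks 48 and 50, otherwise 4 weeks) and the carry-forward example in section 4.2.

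**Formula.** Weeks on escape at the Week 96 (or later) visit = max(96 − Escape Week 0, 12).

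| Flare at Week | No lag | 2-week lag |
|---|---|---|
| 50 | 96 − 50 = 46 | 96 − 52 = 44 |
| 52 | 44 | 42 |
| 60 | 36 | 34 |
| 72 | 24 | 22 |
| 80 | 16 | 14 |
| 84 or later | 12 | 12 (floor) |

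The range is 12 to 44 weeks with the full lag and 12 to 46 without it. Ratios: 44/12 = 3.7 and 46/12 = 3.8. At Escape Week 12 every subject has 12 weeks, apart from visit windows.

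**Does duration also differ by arm?** The SAP gives no flare timing by arm, so this needs an assumption. Flare times were simulated from a Weibull distribution with the same shape in all arms, matched to the no-flare proportions in section 2.4 (45% placebo, 75% Q4W, 80% Q2W), with a 2-week lag. Mean weeks on escape:

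| Weibull shape (assumed) | Placebo | Q4W | Q2W | Placebo − Q2W |
|---|---|---|---|---|
| 0.5 | 32.3 | 30.6 | 30.3 | 2.0 |
| 1 | 25.2 | 23.6 | 23.4 | 1.8 |
| 2 | 18.2 | 17.3 | 17.2 | 1.0 |

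The gap between arms is about 1 to 2 weeks, small beside the spread of more than 30 weeks among subjects.

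**The case against.** The strongest reply is that nothing is lost. Section 8.3.3 tabulates the same variables by visit, in the same Flared Set and by randomised group, and Escape Week 12 is one of those visits under section 3.3. The 12-week result will be reported, only under a different label. The section 8.2.3 summaries are also purely descriptive, with no model, test or alpha. All of this stands, and it limits the severity. It does not remove the contradiction: the tables that carry the secondary label show a visit other than the one in the definition.

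A reader might go further and infer that time on escape differs materially between arms, so that the by-arm columns confound treatment with duration. The documents do not support that. More flares on placebo does not mean earlier flares, and a large gap would need an assumption about timing that the SAP does not make. The arm difference that the SAP does document is another one: under section 2.3.3, full-dose subjects who flare stay on their allocation, so their column shows no re-initiation.

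A reader might also object that "All summaries will be based on observed case data and will use the FS", and ask for non-responder imputation. Section 4.2 does apply that method to the listed binary endpoints in general, but it states separately that post-flare summaries are observed case without adjustment. That is a declared choice. Nor is the method universal in this SAP: section 8.2.2.3 exempts the ASDAS activity levels. For those four mutually exclusive states it would not say which state a missing subject joins.

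**Conclusion.** The contradiction is real and internal to the SAP. Sections 2.2.1.2.3 and 3.3 say Escape Week 12, sections 8.2.3.1 and 8.2.3.2 say Week 96 (or later), and section 3.10 is silent. The MRI schedule in section 3.2.4, which includes Escape Weeks 0 and 12, fits the definition. The protocol is not at hand, so I cannot say which time point its own analysis text uses; the conclusion does not depend on that.

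Followed as written, the secondary tables pool 12 to about 44–46 weeks of escape treatment, up to about 3.8-fold, in place of a fixed 12 weeks. The upper end rests on a single-visit flare at the first scheduled assessment, Week 50; an unscheduled ASDAS before then could move it slightly. How many subjects lie near each end is unknown, because the SAP gives no distribution of flare times.

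This should be fixed. It does not touch the primary analysis, any p-value or any power figure, and it supports no conclusion about differences between arms or about missing-data handling.

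**What to change.** In sections 8.2.3.1 and 8.2.3.2, name Escape Week 12 as the time point of the secondary summaries. Keep Week 96 (or later) as an additional summary, and show time on escape treatment beside it (for example median and range by randomised group) so that the figure can be read for what it is.

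If the sponsor does intend Week 96 (or later) as the secondary time point, the alternative is to declare and justify that in section 3.10 and to amend sections 2.2.1.2.3 and 3.3 to match. Either way, settle it before unblinding.

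The cost is SAP wording and table shells. Escape Week 12 data are already collected, and the by-visit summaries for section 8.3.3 already require them to be programmed.

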#### **8.2.3.2 Binary secondary efficacy variables**

The number and percentage of subjects in the ASDAS disease activity levels (ASDAS-ID, ASDAS-LD, ASDAS-HD, ASDAS-vHD) as well as the number and percentage of subjects achieving ASDAS clinical improvement (ASDAS-CII, ASDAS-MI), and ASAS response (ASAS20, ASAS40, ASAS5/6, and ASAS PR) will be summarized at the Week 96 (or later) visit by randomized treatment group.

### **8.3 Other efficacy variables**

#### **8.3.1 Part A**

##### **8.3.1.1 ASDAS disease activity (ASDAS-ID, ASDAS-LD, ASDAS-HD and ASDAS-vHD) and clinical improvement (ASDAS-CII, ASDAS-MI)**

The number and percentage of subjects in each of the 4 ASDAS disease activity levels will be presented for each visit by axSpA subpopulation and for all subjects combined. These summaries will be produced for the OLS using observed case data and will be repeated using LOCF imputation for missing data.

The number and percentage of subjects achieving ASDAS-MI and ASDAS-CII will be summarized in frequency tables for each visit by axSpA subpopulation and for all subjects combined. These summaries will be produced for the OLS using observed case data and will be repeated using NRI data.

##### **8.3.1.2 ASAS20, ASAS40, ASAS5/6, and ASAS PR response**

Frequency tables will be produced to show the number and percentage of responders for each ASAS endpoint for each visit by axSpA subpopulation and for all subjects combined. These summaries will be produced for the OLS using observed case data and will be repeated using NRI data.

### **8.3.1.3      ASDAS, BASDAI, and BASMI**

Summary statistics of actual values and change from Part A Baseline values will be used to summarize each score (ASDAS, BASDAI, and BASMI) for each visit by axSpA subpopulation and for all subjects combined. These summaries will be produced for the OLS using observed case data and will be repeated using LOCF imputation for missing data.

### **8.3.1.4      SIJ SPARCC and spine ASspiMRI-a in the Berlin modification scores**

Summary statistics of the actual values and change from Part A Baseline values will be used to summarize the SIJ SPARCC and Spine ASspiMRI-a in the Berlin modification scores for each visit by axSpA subpopulation and for all subjects combined. The analysis will use results of the single read assessments for Part A from the independent reviewer. These summaries will be produced for the OLS using observed case data only.

### **8.3.1.5      Individual ASAS core components**

Summary statistics of the actual values and change from Part A Baseline values will be used to summarize the ASAS core components for each visit by axSpA subpopulation and for all subjects combined:

- PtGADA
- Total spinal pain (NRS)
- BASFI
- Average of Questions 5 and 6 of the BASDAI concerning morning stiffness

These summaries will be produced for the OLS using observed case data and will be repeated for BASFI and PtGADA using LOCF imputation for missing data.

### **8.3.1.6      PhGADA**

Summary statistics of the actual values and change from Part A Baseline values will be used to summarize PhGADA for each visit by axSpA subpopulation and for all subjects combined. These summaries will be produced for the OLS using observed case data.

### **8.3.1.7      Nocturnal spinal pain (NRS)**

Summary statistics of the actual values and change from Part A Baseline values will be used to summarize nocturnal spinal pain for each visit by axSpA subpopulation and for all subjects combined. These summaries will be produced for the OLS using observed case data and will be repeated using LOCF imputation for missing data.

### **8.3.1.8      Fatigue (NRS) (from BASDAI)**

Summary statistics of the actual values and change from Part A Baseline values will be used to summarize fatigue item score of the BASDAI for each visit by axSpA subpopulation and for all subjects combined. This summary will be produced for the OLS using observed case data and will be repeated using LOCF imputation for missing data.

The remaining components of the BASDAI maybe analyzed as well.

### **8.3.1.9 BASDAI50 response**

Frequency tables will be produced to show the number and percentage of BASDAI50 responders for each visit by axSpA subpopulation and for all subjects combined. This summary will be performed on the OLS using observed case data and will be repeated using NRI data.

### **8.3.1.10 C-reactive protein (CRP)**

Summary statistics of the actual values, change from Part A Baseline values and the ratio of post-Baseline over Part A Baseline values will be used to summarize the CRP values for each visit by axSpA subpopulation and for all subjects combined. This summary will be produced for the OLS using observed case data and will be repeated using LOCF imputation for missing data.

The geometric mean and the corresponding CV of the geometric mean will be computed and displayed for the observed values and for the ratio of post-Baseline over Part A Baseline values.

### **8.3.1.11 Ankylosing Spondylitis Quality of Life (ASQoL)**

Summary statistics of the actual values and change from Part A Baseline values will be used to summarize the ASQoL score for each visit by axSpA subpopulation and for all subjects combined. This summary will be produced for the OLS using observed case data.

### **8.3.1.12 Work Productivity Survey (WPS)**

Frequency tables will be produced to summarize the answer provided to question 1 of the WPS for each visit by axSpA subpopulation and for all subjects combined.

Summary statistics of the actual values and change from Part A Baseline values will be used to summarize the answers to the question 2 to 9 of the WPS for each visit by axSpA subpopulation and for all subjects combined.

These summaries will be produced for the OLS using observed case.

### **8.3.1.13 EuroQoL Health Status Questionnaire 5 dimensions 3 levels (EQ-5D-3L)**

Frequency tables will be produced to summarize answers provided to each of the 5 items of the EQ-5D-3L for each visit by axSpA subpopulation and for all subjects combined.

Summary statistics of the actual values and change from Part A Baseline values will be used to summarize the EQ-5D-3L VAS score for each visit by axSpA subpopulation and for all subjects combined.

These summaries will be produced for the OLS using observed case data.

### **8.3.1.14 Maastricht Ankylosis Spondylitis Enthesitis Score (MASES)**

Summary statistics of the actual values and change from Part A Baseline values will be used to summarize the MASES score for each visit by axSpA subpopulation and for all subjects combined. This summary will be produced for the OLS using observed case data.

### **8.3.1.15 Swollen and tender joint counts (44 joint count)**

Summary statistics of the actual and change from Part A Baseline values will be used to summarize TJC and SJC for each visit by axSpA subpopulation and for all subjects combined. These summaries will be produced for the OLS using observed case data.

### **8.3.1.16 Spinal mobility**

Summary statistics of the actual and change from Part A Baseline values will be used to summarize spinal mobility as assessed by occiput to wall distance and spinal mobility as assessed by chest expansion for each visit by axSpA subpopulation and for all subjects combined. These summaries will be produced for the OLS using observed case data.

### **8.3.1.17 Number of uveitis flares, IBD exacerbations and psoriasis exacerbations**

Separate tables will be produced to summarize incidence of each of these events (uveitis flares, IBD exacerbations and psoriasis exacerbations) during Part A.

These summary tables will display the number and percentage of subjects experiencing the considered event in Part A and number of event. In this style of output, “number of event” will include all occurrences of the event including repeat occurrences in individual subjects, while “number of subjects” will count each subject only once.

The presentation will be based on the OLS by axSpA subpopulation and overall using observed case data.

For each of these events (uveitis flares, IBD exacerbations and psoriasis exacerbations), the summary table will be repeated based on the subset of subjects with a current occurrence of the event at screening.

### **8.3.1.18 Fecal calprotectin**

Actual fecal calprotectin levels and corresponding change from Part A Baseline values will be summarized by axSpA subpopulation and overall for each visit at which stool samples were taken during Part A using the geometric mean, 95% CI, geometric CV, arithmetic mean, arithmetic SD, median, minimum, and maximum. This analysis will be performed on observed case data only using the OLS.

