## **3           DATA ANALYSIS CONSIDERATIONS**

### **3.1       General presentation of summaries and analyses**

Statistical analysis and generation of tables, figures, and listings will be performed using SAS® Version 9.3 or higher.

Frequency tables (frequency counts and percentages) will be presented for categorical data. If there are missing values, either a missing category will be included in the display or the number of non-missing results will be used for calculations.

In case imputation was performed, summary statistics will not utilize the 'n' (number of available measurements). In addition, for the primary variables and selected outputs the 95% confidence interval (CI) based on the Exact Binomial distribution will be presented.

In general percentages will be calculated based on the utilized analysis set, however in case only subsets are affected, the N of the subset will be used as denominator.

Unless otherwise noted, all percentages will be displayed to 1 decimal place. No percentage will be displayed for zero counts, and no decimal will be presented when the percentage is 100%.

Continuous variables will be summarized with n (number of available measurements), arithmetic mean, standard deviation (SD), median, minimum, and maximum (with 25th and 75th percentiles where specified). For CZP plasma concentration levels and CRP observed values and ratio of post-Baseline over Baseline values the geometric mean and the corresponding coefficient of variation (CV) will be presented. The CV will be calculated as

$$CV = \sqrt{e^{std \ln^2} - 1} * 100$$

where "std ln" represents the standard deviation of the natural logarithm transformed parameter.

The mean, SD, and median will be displayed to 1 more decimal place than collected in the electronic Case Report Form (eCRF). Minimum and maximum values will be displayed to the same level of precision as collected in the eCRF. Unless otherwise specified, all statistical hypothesis tests will be 2-sided and the level of significance for all tests will be 0.05. P-values will be displayed to 3 decimal places.

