### **8.3.1.19 Serum calprotectin**

Actual serum calprotectin levels and corresponding change from Part A Baseline values will be summarized by axSpA subpopulation and overall for each visit at which stool samples were taken during Part A using the geometric mean, 95% CI, geometric CV, arithmetic mean, arithmetic SD, median, minimum, and maximum. This analysis will be performed on observed case data only using the OLS.

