### 8.3.2.12 Descriptive summaries of other efficacy variables

The below listed efficacy variables will be summarized descriptively by visit and by treatment group as applicable using observed case based on the RS unless otherwise specified.

- ASDAS disease activity (ASDAS-ID, ASDAS-LD, ASDAS-HD and ASDAS-vHD)
- Change from Part A Baseline and change from Part B Baseline in SIJ SPARCC and spine ASspiMRI-a in the Berlin modification scores (summaries based on observed case data only)
- Change from Part A Baseline and change from Part B Baseline in PhGADA
- Change from Part A Baseline and change from Part B Baseline in nocturnal spinal pain (NRS)
- CRP (actual values, change from Part A Baseline values, change from Part B Baseline values, ratio of post-Baseline over Part A Baseline values, ratio of post-Baseline over Part B Baseline values)
- Health status as assessed by the EQ-5D-3L: domains, VAS actual score, change from Part A Baseline and change from Part B Baseline in VAS score
- Change from Part A Baseline and change from Part B Baseline in MASES
- Change from Part A Baseline and change from Part B Baseline in swollen and tender joint counts (44 joint counts). The summaries for TJC will be repeated including only the subjects with a TJC>0 at Part A Baseline or Part B Baseline, as appropriate. Similar approach will be used for SJC.
- Change from Part A Baseline and change from Part B Baseline in spinal mobility as assessed by occiput to wall distance and in spinal mobility as assessed by chest expansion
- Change from Part A Baseline and change from Part B Baseline in fecal calprotectin (summaries based on observed case data only)
- Change from Part A Baseline and change from Part B Baseline in serum calprotectin (summaries based on observed case data only)
- Change from Part A Baseline and change from Part B Baseline in the IBD-Q scores (Global IBD-Q total score, IBD-Q bowel symptoms score, IBD-Q systemic symptoms score, IBD-Q emotional function score and IBD-Q social function score)
- Frequency of IBD-Q responders and IBD-Q remitters (NRI data will be used) using Part A Baseline and Part B Baseline as reference
- Resources utilization: concomitant medical procedures, healthcare provider consultations not foreseen by the protocol, in-patient hospitalizations and emergency room visits

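### Geometric mean, its CI and geometric CV are specified for change from Part A Baseline in fecal and serum calprotectin, where they cannot be computed for zero or negative changes

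*SAP*

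**What the plan says.** For fecal calprotectin in Part A, SAP section 8.3.1.18 names two quantities in one sentence: "Actual fecal calprotectin levels and corresponding change from Part A Baseline values will be summarized by axSpA subpopulation and overall for each visit". The statistics follow as a single list, not divided between level and change: "using the geometric mean, 95% CI, geometric CV, arithmetic mean, arithmetic SD, median, minimum, and maximum". Section 8.3.1.19 repeats this for serum ("Actual serum calprotectin levels and corresponding change from Part A Baseline values will be summarized by axSpA subpopulation and overall for each visit"), with the visits described as "for each visit at which stool samples were taken during Part A using the geometric mean".

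Section 3.1 defines the CV as the square root of (e to the power of the squared log-SD, minus 1), times 100, where the log-SD "represents the standard deviation of the natural logarithm transformed parameter". The same section says where geometric statistics are generally used: "For CZP plasma concentration levels and CRP observed values and ratio of post-Baseline over Baseline values the geometric mean and the corresponding coefficient of variation". No difference from baseline is named there.

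For CRP in Part A, section 8.3.1.10 lists actual values, change and ratio. It then limits the geometric mean and CV to certain quantities: "for the observed values and for the ratio of post-Baseline over Part A Baseline values". The SAP defines no calprotectin ratio.

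**The concern.** A change from baseline can be zero or negative, and the logarithm of such a number does not exist. Read literally, the two calprotectin sections ask for statistics that cannot be produced once any subject is unchanged or improved. The SAP does not say whether the cell is then left blank or the subjects are left out.

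The second choice is the harmful one. Keeping only positive changes selects on the outcome: the summary then describes only subjects whose calprotectin rose, and its sign is fixed in advance. The CRP section shows that the SAP makes the right split when it intends one, so the calprotectin wording leaves a real decision to the programmer.

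**Working it through.** The SAP gives no figure to reproduce, because the point is one of definition. The definition is applied first to a small invented example and then to assumed distributions.

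**Formulas.** Geometric mean = exp(mean of ln x). Geometric CV = sqrt(exp(SD of ln x, squared) - 1) x 100, from section 3.1. Both need x > 0 for every subject.

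**Six invented subjects.**

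| | 1 | 2 | 3 | 4 | 5 | 6 |
|---|---|---|---|---|---|---|
| Baseline | 200 | 150 | 100 | 80 | 60 | 50 |
| Post | 80 | 90 | 100 | 40 | 75 | 30 |
| Change | -120 | -60 | 0 | -40 | +15 | -20 |
| Ratio | 0.40 | 0.60 | 1.00 | 0.50 | 1.25 | 0.60 |

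- Arithmetic mean change: -225/6 = -37.5. Median: (-40 - 20)/2 = -30.
- ln(change) is undefined in 5 of 6 subjects. Over what remains, the geometric mean change is exp(ln 15) = +15, from one subject. No log-SD, and so no CV or CI, can be formed from it.
- Geometric mean ratio: the product of the six ratios is 0.09, and 0.09^(1/6) = 0.67, using all six subjects.

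**Assumed distributions (none of these inputs is in the SAP).** Levels are log-normal with baseline geometric mean 100, log-SD s = 0.5 or 1.0, within-subject log correlation rho = 0.3 or 0.6, and true post/baseline ratio r = 1.0, 0.8 or 0.5. There are 200,000 simulated pairs per setting. Ranges run over the four combinations of s and rho.

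| r | Share with change > 0 | Geometric mean change, positives only | Arithmetic mean change, all | Median change, all | Geometric mean ratio, all |
|---|---|---|---|---|---|
| 1.0 | about 50% | +24 to +66 | about 0 | about 0 | 1.00 |
| 0.8 | 31% to 43% | +17 to +53 | -23 to -33 | -14 to -19 | 0.80 |
| 0.5 | 6% to 28% | +8 to +34 | -57 to -83 | -39 to -47 | 0.50 |

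The shares agree with the closed form P(change > 0) = Phi(ln r / (s x sqrt(2(1 - rho)))). For r = 0.5, s = 0.5, rho = 0.6 this is Phi(-0.693/0.447) = Phi(-1.55) = 0.061. For r = 0.5, s = 1.0, rho = 0.3 it is Phi(-0.693/1.183) = Phi(-0.586) = 0.28.

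The positives-only value is above zero in every row, including the row with no true change. The ratio recovers the true value with every subject included.

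**The case against.** The strongest reply is that little is lost. The same list includes the arithmetic mean, SD, median, minimum and maximum, all of which are valid for a change, and the median is robust to skewness and keeps the right sign. The geometric means of actual levels are also valid. In the six-subject example they are 94.7 at baseline and 63.4 afterwards, and 63.4/94.7 = 0.67 is the relative fall (without a paired CI). A positive geometric mean change beside a negative median would look like a fault, not a finding. All of this stands and limits the point.

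Several stronger readings are tempting, but the SAP does not support them:

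- **That the table would show calprotectin rising on CZP.** This needs the software to drop non-positive changes, which the SAP does not say. A blank cell fits the text equally well.
- **That most changes will be negative.** Section 3.2.19 describes calprotectin only as a marker of inflammation and gives no expected change. The undefined statistic does not depend on this: with no true change, about half the subjects are already affected.
- **That Part B and the Escape Part share the error.** Section 8.3.2.12 says only "Change from Part A Baseline and change from Part B Baseline in fecal calprotectin (summaries based on observed case data only" and names no geometric statistics. The defaults in section 3.1 apply and are valid for a change. Section 8.3.3 mirrors that format.
- **That serum results would be lost.** This holds only if serum was drawn at visits without stool, and the sampling schedule is not in the SAP. Sections 8.3.1.21 and 8.3.2.10 correlate fecal with serum values at Part A Baseline, Week 48 and Week 96, so the plan expects both there.

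The reply that geometric statistics were obviously meant for levels only does not stand. The sentence does not say so, and section 8.3.1.10 shows how the SAP writes that restriction when it means it.

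**Conclusion.** The specification is wrong as written. In sections 8.3.1.18 and 8.3.1.19 the geometric mean, its 95% CI and the geometric CV of change from Part A Baseline cannot be computed once any change is zero or negative. If such changes are dropped, the value is positive by construction. The first statement follows from the definition alone. The second depends on that way of handling them, and its size depends on the assumed distributions above. The 95% CI is read as belonging to the geometric mean, which it directly follows in the list.

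The reach is small: a few cells of a descriptive, open-label Part A summary of an other efficacy variable, with no test attached. No primary or secondary result is touched. The stool wording in the serum section is a slip with no demonstrated loss of data.

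**What to change.** In sections 8.3.1.18 and 8.3.1.19, restrict the geometric mean, 95% CI and geometric CV to actual levels and to the ratio of post-Baseline over Part A Baseline, matching section 8.3.1.10. Summarise absolute change by arithmetic mean, SD, median, minimum and maximum. In section 8.3.1.19, refer to serum samples in place of stool samples.

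Adding calprotectin ratios in sections 8.3.2.12 and 8.3.3 is optional. It would bring Part B and the Escape Part into line with CRP, but it corrects no error.

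The cost is a wording change and one derived variable per marker, from data already collected.
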